3. PROTOCOL SYNOPSIS

[figure not shown]
Test Drugs:	Proellex® (Telapristone Acetate): 6 and 12 mg gelatin capsules and matching placebo
Protocol Number:	ZPE-202
Study Purpose:	To determine the safety and efficacy of two doses of Proellex in premenopausal women with pelvic pain in confirmed endometriosis patients.
Study Design and Duration Of Treatment:	This study is a phase 2, 3-arm-study with an 18 week active dosing period. The study will be conducted in two stages. In the first stage, women will receive daily single blind dosing with placebo, for at least one full menstrual cycle. Endometriosis pain, dysmenorrhea, non-menstrual pelvic pain and dyspareunia (BBSS) as well as use of pain medications and vaginal bleeding intensity will be recorded using an electronic diary. Following the placebo run-in phase, subjects will be randomized into one of 3 arms in a 1-1-1 fashion weighted by a combined BBSS and analgesic score. The start of the 18 week dosing period in the double-blind phase should commence as soon after ovulation as possible, after which subjects will be followed until menses has returned. During the follow-up period subjects will continue to record study information in the electronic diary. The final follow-up visit should be scheduled after blood flow has stopped. [REDACTED]
Subject Population:	The study will enroll healthy adult, non-obese pre-menopausal women with surgically confirmed endometriosis.
Number of Subjects:	Up to 60 female subjects, 20 per dose arm
Number of Sites	Approximately 10 sites in the US
Study Duration:	Total participation in the study is approximately 6-7 months. [REDACTED]

[figure not shown]
Study Endpoints	
• The primary efficacy endpoint will be percent change in daily average combined BBSS patient reported scores comparing the baseline menstrual cycle to a similar period leading up to the last day of dosing (Week 18)• The secondary endpoints will be
➢ Change in daily average use of analgesics from the baseline menstrual cycle to the matching end-of- study period➢ Change in BBSS score incorporating the two physician reported scores➢ Change in the individual BBSS scores of the three patient reported outcomes➢ Change in number of days and intensity of menstrual or non-menstrual vaginal bleeding.
Statistical Methods:	
Summaries for quantitative variables include the sample size, mean, median, standard deviation, minimum, and maximum. Summaries for categorical variables include the number and percent of patients for each outcome. All summaries will be prepared for each treatment group.
 
Summaries will be prepared for each treatment group of subject accountability, baseline demographic, and medical history data.
 
The primary efficacy variable is the change in the subject reported outcomes of the BBSS from the baseline period to a comparable period leading up to the end of dosing. An overall comparison among the 3 treatment groups will be performed.
 
The secondary efficacy variables will be treated similarly.

[figure not shown]
[figure not shown]
5. LIST OF ABBREVIATIONS

AE	Adverse event
PBAC	Pictorial Bleeding Assessment Chart
BBSS	Biberoglu Behrman symptom severity scale
C_{avg}	Average concentration
C_{max}	Maximum concentration
CRF	Case report form
DHEA	Dehydroepiandrosterone
dL	Deciliter
ECG	Electrocardiogram
FSH	Follicle-stimulating hormone
GCP	Good Clinical Practice
GnRH	Gonadotrophin releasing hormone
g	Grams
hCG	Human chorionic gonadotrophin
ICH	International Conference on Harmonization
IGF-1	Insulin-like growth factor-1
IRB	Institutional Review Board
IND	Investigational new drug
IUD	Intra-uterine device
kg	Kilogram(s)
LD ₅₀	Median lethal dose
LH	Luteinizing hormone
m	Meters
mg	Milligram(s)
mL	Milliliter
ng	Nanograms
PCOS	Polycystic Ovarian Syndrome
PK	Pharmacokinetic
PRL	Prolactin
PSA	Prostate specific antigen
RBC	Red blood cell
SAE	Serious adverse event
SHBG	Sex hormone binding globulin
TT	Total testosterone
UFSQOL	Uterine Fibroid Symptoms Quality of Life Questionnaire
WBC	White blood cell

[figure not shown]
[figure not shown]
[figure not shown]
6. BACKGROUND INFORMATION

6.1 Rationale for Current Study

Repos believes telapristone offers the potential to provide significant symptomatic relief to women that suffer from a variety of reproductive disorders in which progesterone may be implicated. Most notably the sponsor has seen significant clinically relevant impact on the symptoms of both uterine fibroids and endometriosis.

sponsor believes there is a direct correlation of symptomatic relief for uterine

[figure not shown]

27AUG2018 Abbreviated CSR ZPE-202

FDA Guidance For Liver Enzyme Elevation Characterization as SAE

- 1. LFTs \geq 8 x ULN
- 2. LFTs \geq 5 x ULN for 2 consecutive weeks
- 3. LFTs \geq 3 x ULN + Bilirubin 2 x ULN
- 4. LFTs \geq 3 x ULN + clinical signs or symptoms (nausea; jaundice; etc.)

[REDACTED]

6.5 Ethical Conduct of the Study

This trial will be conducted in strict compliance with the protocol and all applicable FDA regulations and GCP guidelines to insure Good Clinical Practice standards. The Institutional Review Board (IRB) for this study is IntegReview, [name].

6.6

[REDACTED]

[REDACTED]

7. TRIAL OBJECTIVES AND PURPOSE

The primary objective of this study is to determine the safety and efficacy of two oral doses of Proellex administered for 18 weeks to premenopausal women with confirmed endometriosis.

8. TRIAL DESIGN

[figure not shown]
8.1 Study Endpoints

The Primary endpoint will be:

- Percent change in daily average combined BBSS patient reported scores comparing the baseline menstrual cycle to a similar period leading up to the last day of dosing (Week 18)

The Secondary endpoints will be:

- Change in daily average use of analgesics from the baseline menstrual cycle to the matching end-of- study period
- Change in BBSS score incorporating the two physician reported scores
- Change in the individual BBSS scores of the three patient reported outcomes
- Change in number of days and intensity of menstrual or vaginal bleeding

8.2 Study Design

8.2.1 Overview of Study Design

This study is a phase 2, 3-arm-study with an 18 week active dosing period. The study will be conducted in 2 stages. In the first stage, women will receive a daily single-blind placebo. This stage will last as long as it takes to record at least one full menstrual cycle (ovulation until ovulation). Daily patient reported scores for the three elements of endometriosis pain, dysmenorrhea, non-menstrual pelvic pain and dyspareunia will be recorded using an electronic diary with prompts replicating a modified Biberoglu and Behrman symptom severity score

(BBSS).

Following the run-in phase, 60 subjects will be randomized into one of 3 arms in a 1-1-1 fashion weighted by a combined BBSS and analgesic score.

The start of dosing in the double-blind phase should commence as soon as possible after ovulation following the end of the previous menstrual event. Once the 18 week active dosing period is completed, subjects will be followed until menses has returned (usually within 35 days or less). The follow-up visit should be scheduled after blood flow has stopped. During the follow-up period subjects will continue to record study information in the electronic diary.

8.2.2 Study Drug Accountability

The designee assigned by the Principal Investigator at each site will maintain accurate records of receipt of all study drugs, including dates of receipt. Reasons for deviation from the expected dispensing regimen must also be recorded. A Drug Dispensing Form will be provided for this purpose. To satisfy regulatory requirements regarding drug accountability and destruction, the Principal Investigator at each site will return all used or unused empty and partially used study medication with dispensing records to the Sponsor for final accountability and disposal, after accountability has been verified by the study monitor.

8.2.3 Randomization and Blinding

All subjects will receive placebo from Visit 1 until Visit 3. At Visit 3, subjects will be randomized to treatment in Arms 1, 2, or 3 and will be treated with one capsule daily of 6 mg or 12 mg of Proellex, or placebo, which will be administered for 18 weeks. Blinded treatments kits will be randomized and distributed by the packaging company.

8.2.4 Study Medication

All study drugs will be supplied by Repros Therapeutics Inc. Test drug, Proellex, [REDACTED] and will be

packaged by a clinical supplies contract vendor designated by Repros Therapeutics Inc. The placebo [REDACTED] and will be packaged by the same clinical supplies contract vendor. Active and matching placebo capsules will be bottled in identical packaging. Each bottle will have a label containing bottle number, number of capsules, expiration date, clinical use only and instructions to take 1 capsule daily in the morning approximately one hour before breakfast. Subjects will take one capsule with approximately 8 ounces of water and study medication should be taken roughly at the same time every day. Subjects will record study medication date and time on subject electronic drug diary cards. [REDACTED]
[REDACTED]
[REDACTED]

8.3 Selection and Withdrawal of Subjects

Subjects for the study will be selected during screening based on the inclusion and exclusion criteria and clinical assessments listed below. Subjects will be discontinued from the study prematurely if:

- Unacceptable adverse events occur considered by the investigator to be associated with use of the study drug
- The subject requests to be withdrawn from the study
- LFT elevation >3 times upper limit of normal
- ALT > upper limit of normal for 3 successive weeks
- A need arises for concomitant medication prohibited by the protocol
- The Principal Investigator decides that it is in the subject's best interest
- The subject is noncompliant with the protocol
- Any subject who develops an endometrial thickness \geq 20 mm and experiences heavy bleeding for 7 days or more will be discontinued from the study. Appropriate follow up treatment will be provided as deemed necessary by the investigator.

8.3.1 Inclusion Criteria

Subjects must meet the following criteria:

- Healthy adult females between 18 and 47 years of age with surgically confirmed diagnosis of endometriosis (within-10 years). A laparoscopic diagnosis is acceptable.
- Normal or abnormal but non-clinically significant transvaginal ultrasound
- History of menstrual events occurring in regular cycles

[figure not shown]
- Agreement not to attempt to become pregnant during the trial
- Agreement to limit alcohol consumption to no more than 2 drinks per week and to avoid alcohol consumption within 48 hours before each visit
- Ability to complete a daily electronic subject diary and study procedures in compliance with the protocol
- Agrees to use a double-barrier contraceptive over the course of the study
- Has a negative pregnancy test at the Screening and Baseline visits, and subsequent study visits
- A Body Mass Index (BMI) between 18 and 39 inclusive
- Is available for all treatment and follow-up visits

[figure not shown]
8.3.2 Exclusion Criteria

[figure not shown]
Subjects meeting any of the following criteria will be excluded from the study:

- Subject is a post-menopausal woman, defined as either; six (6) months or more (immediately prior to screening visit) without a menstrual period, or prior hysterectomy and/or oophorectomy.
- Subject is pregnant or lactating or is attempting or expecting to become pregnant [REDACTED]
- [REDACTED]
- Women with abnormally high liver enzymes or liver disease. (ALT or AST exceeding 1.5x ULN AND total bilirubin exceeding 1.5xULN at screening and confirmed on repeat).
- Received an investigational drug in the 30 days prior to the screening for this study
- Women with a history of PCOS
- Concurrent use of any testosterone, progestin, androgen, estrogen, anabolic steroids, DHEA or hormonal products for at least 2 weeks prior to screening and during the study.
- Use of oral contraceptives in the preceding 30 days. Use of Depo-Provera® in the preceding [REDACTED]
- Use of GnRHs (e.g. Lupron Depot) within 3 months of the first dose of study drug (Lupron Depot must have a wash-out period of 3 months after the period of duration of the Lupron dose).

- Has an IUD in place
- Presence of intramural fibroids that impact the endometrial stripe, submucosal fibroids (any size), or endometrial polyps. Subserosal and intramural fibroids with no impact on the endometrial stripe are acceptable.
- Present history or condition that causes non-endometriosis related dyspareunia (e.g. vulvar vestibulitis).
- Past or present history of thrombophlebitis or thromboembolic disorders.
- Known or suspected carcinoma of the breast or reproductive organs.
- History of abnormal ECG that, in the opinion of the investigator, is clinically significant and will prevent the subject from completing the study, including a QTc of greater than 450 ms.
- Cervical dysplasia classified as Atypical Squamous Cells of Undetermined Significance (ASCUS) associated with high-risk human papilloma virus (HPV) or Low/High Grade Squamous Intraepithelial Lesion (LGSIL or HGSIL).
- History of abnormal endometrial biopsy including the presence of EIN.
- Recent history (within past 6 months) of alcoholism or drug abuse.
- Known active infection with HIV, Hepatitis A, B or C.
- Previous history of auto-immune disease and/or positive antinuclear antigen (ANA).
- Endometrial stripe ≥ 18 mm in thickness at Visit 1.
- Women currently taking cimetidine or spironolactone.
- Clinically significant abnormal findings on screening examination and laboratory assessments or any condition which in the opinion of the investigator would interfere with the participant's ability to comply with the study instructions or endanger the participant if she took part in the study..

10. ASSESSMENT OF EFFICACY

10.1 Primary Endpoint

[figure not shown]
The Primary endpoint will be:

- The percent change in daily average combined BBSS patient reported scores comparing the baseline menstrual cycle to a similar period leading up to the last day of dosing (Week 18)

10.2 Secondary Endpoints

The Secondary endpoints will be:

- Change in daily average use of analgesics from the baseline menstrual cycle to the matching end-of- study period
- Change in BBSS score incorporating the two physician reported scores
- Change in the individual BBSS scores of the three patient reported outcomes
- Change in number of days and intensity of menstrual or vaginal bleeding.

[REDACTED]

11.1 Adverse Events

11.1.1 Reporting Adverse Experiences

Any AE (clinical sign, symptom, or disease) temporally associated with the use of this investigational drug, whether or not considered related to the investigational product, shall be documented on the CRF. All AEs reported by the subject or observed by the Principal Investigator will be individually listed. The signs and symptoms, time of onset (24-hour clock), duration, action taken and follow-up procedures will be reported.

11.1.2 Definitions

Adverse Event – Any untoward medical occurrence in a clinical investigation subject administered a drug and does not necessarily have a causal relationship with this treatment. An AE can therefore, be any unfavorable and unintended sign (including an abnormal laboratory finding), symptom, or disease temporally associated with the use of an investigational product, whether or not related to the investigational product.

Serious Adverse Event (SAE) – An adverse drug experience that results in any of the following outcomes: death, a life-threatening experience, requires or prolongs subject hospitalization, results in persistent or significant disability/incapacity, or is a congenital anomaly or birth defect.

Unexpected Adverse Event: Any adverse event that is not identified in nature, severity, or frequency in the current Investigator's Brochure.

Additionally, the Principal Investigator will evaluate all AEs as follows:

Action taken: whether or not the AE caused the subject/patient to discontinue the study medication.

Intensity, to be graded as:

DEGREE	DESCRIPTION
Mild	Awareness of signs and symptoms; easily tolerated
Moderate	Discomfort sufficient to interfere, but not prevent daily activity
Severe	Unable to carry out usual activity

Relationship to study medication, to be graded as:

DEGREE	DESCRIPTION
Definitely	There is evidence of exposure to the study drug, for example, reliable history or acceptable compliance assessment; the temporal sequence of the AE onset relative to the medication is reasonable; the AE is most likely to be explained by the treatment than by another cause; the AE shows a pattern consistent with previous knowledge of the treatment.
Probably	There is evidence of exposure to the study drug; the temporal sequence of the AE onset relative to medication administration is reasonable; the AE is more likely explained by the treatment than by another cause.
Possibly	There is evidence of exposure to the study drug; the temporal sequence of the AE relative to the medication administration is reasonable; the AE could have been due to another equally likely cause.
Probably not	There is evidence of exposure to the study drug; there is another more likely cause of the AE.
Definitely not	The subject/patient did not receive the study drug; or temporal sequence of the AE onset relative to administration of the study drug is not reasonable; or there is another obvious cause of the AE.

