- The decision to withdraw from the study because of an adverse event, including pain from endometriosis or from another condition, is decided by the subject and the investigator or her personal physician. The event, and any treatment should be recorded in the study records.

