10. ASSESSMENT OF EFFICACY

10.1 Study Endpoints

Primary Endpoint

- Change and percent change in the individual BBSS scores of the three patient reported outcomes (dysmenorrhea, dyspareunia and non-menstrual pelvic pain) by study visit and treatment cycle.

Secondary Endpoints

- Change in daily average use and percent change of prescription medications from the baseline menstrual cycle to the matching period leading up to Week 18, the last day of dosing of the first cycle of treatment.
- Change in daily average use and percent change of over the counter medications from the baseline menstrual cycle to the matching period leading up to Week 18, the last day of dosing of the first cycle of treatment, calculated based on days with reported values.
- Change in daily average use and percent change of overall medication use, prescription and over the counter, from the baseline menstrual cycle to the matching period leading up to Week 18, the last day of dosing of the first cycle of treatment, calculated based on days with reported values.
- Change and percent change in BBSS score incorporating the two physician-reported scores by study visit and treatment cycle.
- Change from baseline in endometrial pain assessed using a Visual Analog Scale (VAS) by study visit and treatment cycle.
- Change from baseline in daily average dysmenorrhea and non-menstrual pelvic pain using an 11-point numerical rating scale (NRS) by study visit and treatment cycle.

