11.1 Adverse Events

11.1.1 Reporting Adverse Experiences

Any AE (clinical sign, symptom, or disease) temporally associated with the use of this investigational drug, whether or not considered related to the investigational product, shall be documented on the CRF. All AEs reported by the subject or observed by the Principal Investigator will be individually listed. The signs and symptoms, time of onset (24-hour clock), duration, action taken and follow-up procedures will be reported.

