11.1.2 Definitions

Adverse Event – Any untoward medical occurrence in a clinical investigation subject administered a drug and does not necessarily have a causal relationship with this treatment. An AE can therefore, be any unfavorable and unintended sign (including an abnormal laboratory finding), symptom, or disease temporally associated with the use of an investigational product, whether or not related to the investigational product.

Serious Adverse Event (SAE) – An adverse drug experience that results in any of the following outcomes: death, a life-threatening experience, requires or prolongs subject hospitalization, results in persistent or significant disability/incapacity, or is a congenital anomaly or birth defect.

Cases of liver transaminases that increase above 3 times the upper limit of normal must be reported as SAEs regardless of whether the above defined SAE criteria are met.

Unexpected Adverse Event: Any adverse event that is not identified in nature, severity, or frequency in the current Investigator's Brochure.

Additionally, the Principal Investigator will evaluate all AEs as follows:

Action taken: whether or not the AE caused the subject/patient to discontinue the study medication.

Intensity, to be graded as:

DEGREE	DESCRIPTION
Mild	Awareness of signs and symptoms; easily tolerated
Moderate	Discomfort sufficient to interfere, but not prevent daily activity
Severe	Unable to carry out usual activity

Relationship to study medication, to be graded as:

DEGREE	DESCRIPTION
Definitely	There is evidence of exposure to the study drug, for example, reliable history or acceptable compliance assessment; the temporal sequence of the AE onset relative to the medication is reasonable; the AE is most likely to be explained by the treatment than by another cause; the AE shows a pattern consistent with previous knowledge of the treatment.
Probably	There is evidence of exposure to the study drug; the temporal sequence of the AE onset relative to medication administration is reasonable; the AE is more likely explained by the treatment than by another cause.
Possibly	There is evidence of exposure to the study drug; the temporal sequence of the AE relative to the medication administration is reasonable; the AE could have been due to another equally likely cause.
Probably not	There is evidence of exposure to the study drug; there is another more likely cause of the AE.

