6.7.5 BBSS Patient Reported Scores

Patient reported daily BBSS component scores (dysmenorrhea, pelvic pain, dyspareunia) and total score and the change from baseline in each will be summarized from patient diaries.

The statistical significance of the change from baseline within treatment groups will be based on a paired t-test or Wilcoxon signed-rank test, as appropriate. The change from baseline will be compared between groups using a t-test or Wilcoxon rank-sum test, as appropriate.

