6.8.1 Adverse Events (AEs)

Treatment-emergent AEs (TEAEs) are defined as those AEs with an onset date and time equal to or after the start of study medication in stage 2, or those events in which the onset date and time are before the start of study medication but worsened after the start of study medication. To be conservative, in the case of a missing onset time for an AE, an AE with a start date equal to or after the dosing date will be considered treatment-emergent. AE's with missing onset dates will also be considered treatment-emergent.

All TEAEs will be summarized by treatment group. The number of TEAEs as well as the number and percentage of subjects who experienced at least one TEAE will be summarized for each system organ class and each preferred term. The percentage will be based on the number of subjects included in the Safety population. Each subject will contribute at most one count per summarization category.

If a subject has more than one AE that codes to the same preferred term, the subject will be counted only once for that preferred term. Similarly, if a subject has more than one AE within a system organ class category, the subject will be counted only once for that system organ class category.

TEAEs will also be summarized by maximum severity and by strongest relationship to treatment. Serious adverse events (SAEs) will be tabulated and listed in a manner similar to TEAEs. A listing of all AE data will be provided to supplement the tabulated results.

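### Endometriosis pain is the primary efficacy outcome and can also be logged as an adverse event; SAP 6.8.1 should add TEAE summaries with a pre-listed set of pain terms excluded, beside the standard tables.

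*Protocol*

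**What the plan says.** **Efficacy.** The primary endpoint (Protocol 10.1, latest version in the file) is change in the three patient-reported BBSS items. SAP 6.7.5 analyses "Patient reported daily BBSS component scores (dysmenorrhea, pelvic pain, dyspareunia) and total score and the change from baseline".

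**Adverse events.** The definition in Protocol 11.1.2 reads: "An AE can therefore, be any unfavorable and unintended sign (including an abnormal laboratory finding), symptom, or disease temporally associated with the use" (that is, use of the study product). It is generic wording, the same in every protocol version in the file. Protocol 11.1.1 adds that any such event, "whether or not considered related to the investigational product, shall be documented on the CRF". Protocol 8.3, on who decides about withdrawal, speaks of an "adverse event, including pain from endometriosis or from another condition". That sentence came in with Amendment 8US and is kept in the latest version.

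**Tabulation.** SAP 6.8.1 treats an AE as treatment-emergent if it starts at or after the first stage 2 dose, or if it started before and then worsened. On counting it says: "The number of TEAEs as well as the number and percentage of subjects who experienced at least one TEAE will be summarized", by system organ class and preferred term. A woman counts at most once per category. There are further summaries by maximum severity and by strongest relationship, and a listing of all AE data. No test on TEAE rates is visible, and no visible text treats the efficacy symptoms separately.

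**The concern.** The same symptom can enter the trial's results twice, once as an efficacy score and once as a harm. Every participant has symptomatic disease at entry (BBSS of at least 7 at screening, Protocol 8.3.1).

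SAP 6.8.1 offers two routes by which pain can become a TEAE: worsening of an existing event, or an onset after dosing starts. Dysmenorrhea is cyclic, so an episode entered as a new event qualifies by its onset date even if it is no worse than before. The SAP lists becoming amenorrheic among its efficacy endpoints. If the drug works as hoped, such entries would be commoner on placebo.

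At stake are the pooled per-woman rows: any overall TEAE figure, organ classes that contain pain terms, and maximum severity. In those rows a benefit on pain offsets a real excess of other events on drug, so the safety comparison partly carries the efficacy result. With 20 women per arm, single preferred terms will be sparse and readers will lean on the pooled rows.

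**Working it through.** **The plan's own figures.** The documents state no TEAE rate, so there is nothing to reproduce. The one relevant design figure is 20 women per arm (Protocol 13.1). All rates below are assumptions.

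**Model.** Let *h* be the risk of at least one non-pain TEAE and *p* the risk of at least one pain TEAE, taken as independent within a woman. Then P(any TEAE) = 1 - (1 - *h*)(1 - *p*).

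**Step 1: a true excess of 10 points.** *h* = 40% on placebo and 50% on drug; *p* = 5% on drug. Drug: 1 - 0.50 × 0.95 = 52.5%.

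| Placebo *p* | Placebo any TEAE | Drug minus placebo |
|---|---|---|
| 10% | 1 - 0.60 × 0.90 = 46% | +6.5 points |
| 20% | 1 - 0.60 × 0.80 = 52% | +0.5 points |
| 30% | 1 - 0.60 × 0.70 = 58% | -5.5 points |

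**Step 2: larger true excesses.**
- *h* 40% vs 60%, *p* 20% vs 5% (placebo vs drug): 52% vs 62%, so 20 points shrink to 10.
- *h* 40% vs 55%, *p* 40% vs 10%: 64.0% vs 59.5%, so +15 points become -4.5.

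**Step 3: where the sign is lost.** The arms tie when placebo's *p* equals 1 - (1 - *h* drug)(1 - *p* drug)/(1 - *h* placebo).

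| *h* placebo vs drug | Drug *p* = 0% | 5% | 10% |
|---|---|---|---|
| 30% vs 45% | 21.4% | 25.4% | 29.3% |
| 40% vs 55% | 25.0% | 28.8% | 32.5% |
| 30% vs 50% | 28.6% | 32.1% | 35.7% |
| 40% vs 60% | 33.3% | 36.7% | 40.0% |

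For the case in step 1 the tie is at 1 - 0.475/0.60 = 20.8%. Across these scenarios placebo needs a pain-TEAE rate of about 20% to 40% for the excess to cancel. Below that it shrinks but keeps its sign.

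**Step 4: at the trial's size.** Exact binomials, 20 per arm, *h* 40% vs 60%. The chance that placebo's observed any-TEAE rate equals or exceeds the drug's is 13% with no pain TEAEs, 41% with *p* 30% vs 10%, and 57% with *p* 40% vs 10%.

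**Step 5: which rows are touched.** A preferred-term row for a non-pain event contains no pain events, so it does not change in any scenario. Organ classes without pain terms do not change either. In the maximum-severity table, a woman with severe pain and a moderate drug effect appears only as severe. A pain-excluded count of women cannot be derived from preferred-term rows, because those rows do not show which women overlap.

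**The case against.** The other side has several good points.

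- **Unchanged pain is not a TEAE.** A reader might infer that lack of efficacy on placebo by itself inflates placebo's TEAE rate. SAP 6.8.1 does not support that: pain present before dosing counts only if it worsens. Inflation needs worsening, or cyclic episodes entered as new events, together with real relief on drug. This stands, and the point is conditional on it.
- **Diary pain is not shown to become an AE.** Routine pain goes in the daily diary and AEs go on the CRF. The sentence in Protocol 8.3 concerns withdrawal decisions. A reader might infer that every bad pain score is counted twice, but no passage says so. This stands too. The broad definition permits such entries without requiring them, and the visible text leaves it to the site.
- **No explicit any-TEAE percentage.** The stated count rule is by organ class and preferred term. The SAP does say that all TEAEs will be summarised by arm, so an overall row is likely but not spelled out. Organ-class and severity rows are explicit.
- **Harms remain visible.** Non-pain preferred terms are unaffected. With up to 60 women, counts without pain terms could be rebuilt from the AE listing. Pain graded as unlikely to be related would also stay out of the related rows. All true, but choosing the terms after unblinding would carry little weight.
- **Excluding pain from the main tables could hide harm.** If the drug worsened pain in some women, that should be seen. This stands and shapes the fix.

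Protocol section 9, the appendices, some text before Protocol 11.1 and any SAP text after 6.8.1 are redacted or not in the file, so recording guidance there cannot be ruled out.

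**Conclusion.** The overlap between outcome and adverse event is real in the current text, and the visible SAP does nothing to separate the two. Pooled per-woman TEAE rows can therefore carry part of the efficacy result. In the worked cases a true 10-point excess falls to 6.5 points at a 10% placebo pain-TEAE rate, and an excess of 10 to 20 points cancels or reverses at about 20% to 40%.

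These sizes rest on assumed rates, on independence of pain and other events within a woman, on pain being logged as an AE, and on the drug relieving pain. If pain TEAEs cluster in women who already have another TEAE, the shift is generally smaller.

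A reader might go further and conclude that the plan conceals the drug's harms. The documents do not support that: the effect is confined to pooled rows, preferred-term rows and the full listing keep other harms visible, and no visible test or decision rule uses TEAE rates. This is a worthwhile, cheap improvement to the safety display and does not invalidate the safety analysis.

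**What to change.** Before unblinding, add to SAP 6.8.1:

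1. A list of the preferred terms that match the efficacy symptoms: dysmenorrhea, pelvic pain, dyspareunia and endometriosis pain.
2. A statement that the all-events TEAE tables remain the standard display.
3. Beside them, the overall, organ-class, maximum-severity and relationship summaries by arm with the listed terms excluded.
4. A by-arm table of the listed terms alone, so that any worsening of pain on drug stays visible.

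AE collection and SAE reporting do not change. The cost is a short term list and one repeat of tables already planned, with no new data. The downside is a second set of TEAE tables that must be clearly labelled.
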